Subjects: We will recruit 50 healthy volunteers, with the expectation (based on previous retention rates) that 36 healthy volunteers (18 male, 18 female; age range 18-35 years) will complete all experimental procedures. All participants will be recruited without regard to race, religion or ethnicity through posters, advertisements and word-of-mouth referrals. Candidates will be screened in accordance with our general screening protocol, approved by the IRB under Protocol #13681B, which includes a physical, EKG, psychiatric screening interview and detailed drug use history questionnaire. Because CBD will be administered as part of the study, the following populations are excluded for safety reasons: Individuals with a medical condition contraindicating study participation, as determined by our physician, individuals regularly using any medications aside from hormonal contraception in women, individuals with a current (active in the past year) DSM-IV Axis I mood, anxiety, eating, or substance dependence disorder or a lifetime history of a psychotic disorder or mania; women who are pregnant, nursing, or planning to become pregnant in the next 3 months; anyone reporting a known or suspected allergy to cannabinoids. The self-report questionnaires we use require fluency in English, and have not been translated and validated in other languages, thus individuals with less than a high-school education or those not fluent in English will be excluded, as lack of English familiarity at a high school level may compromise our ability to interpret their self-reports. Individuals with a BMI below 19 or above 30 will also be excluded, as this would change dosing requirements. Last, for scientific reasons, we will include only individuals who report using marijuana < 100 times in their lifetime, to reduce variation in possible developed tolerance to CBD.

Drug and Doses: We will administer placebo, 300mg, 600mg and 900mg CBD in counterbalanced order under double-blind conditions. Plasma levels peak approximately 1 - 4 hr after oral administration, with mean peak concentration at 90min, and remain elevated up to 12 hr after an acute dose. The 300mg, 600mg and 900mg doses have been effective doses for reducing anxiety in previous studies (Bergamaschi et al. 2011b; Fusar-Poli P and et al. 2009; Zuardi et al. 1993). Using three doses will help establish a dose-response curve for any effects. Doses will be separated by at least 7 days

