Study Session: Please see below for a full timeline of the study session. Participants will be asked to fast overnight. On study session days, participants will arrive at 9am, and consume a standardized snack. Participants will then complete a urine and breath screening for recent alcohol and drug use, and a pregnancy test (for women). We will then take Time 1 measures of subjective mood, drug effects and cardiovascular variables. We will continue to take these same measures periodically throughout the study (see below). Participants will be administered the drug or placebo at 1:30pm. While waiting for the drug effect to reach peak, participants will be allowed to relax and watch a movie or read a book, but will not be allowed to do work. At 2:15 pm, 3 pm, 3:45 pm, we will reassess mood. The task portion of the study will begin approximately 90min after administration of the drug, and will last for approximately 1 hour, to coincide with the peak effect of the drug. The IAPS, DEIT, ABT tasks will be presented in a counterbalanced order. The psychophysiological equipment will then be disconnected and the IST task will be completed. Participants will then remain in the lab completing subjective measures of the drug effect every half-hour until at least 5:45 pm (when we expect drug effects will be decreased sufficiently to permit participants to leave safely), or until drug effects decrease sufficiently to permit participants to leave safely (as measured by both subjective report and cardiovascular variables). Some drug effects may persist for up to 12hrs after the end of the study session, but based on the literature on CBD given chronically to an ambulatory population, these should be mild and non-impairing (Cunha et al. 1980). Sessions will be separated by at least 5 days.

Timeline

1:00pm	- Arrival, snack, breath and urine tests
1:15pm	- Mood (POMS), drug effect (DEQ, ARCI) and cardiovascular measures
1:30pm	- Capsule administered
2:15pm	- Mood (POMS), drug effect (DEQ, ARCI) and cardiovascular measures
3:00pm	- Mood (POMS), drug effect (DEQ, ARCI) and cardiovascular measures
3:45pm	- Mood (POMS), drug effect (DEQ, ARCI) and cardiovascular measures
4:00pm	- IAPS, DEIT, ABT tasks, counterbalanced
4:45pm	- IST task
5:00pm	- Mood (POMS), drug effect (DEQ, ARCI) and cardiovascular measures
5:45pm	- Mood (POMS), drug effect (DEQ, ARCI) and cardiovascular measures
5:50pm	- Leave laboratory

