Debriefing: Participants will return to the lab for a final session at which they will complete a final DEQ rating of how much they liked each study drug and how much they would want to take each study session drug again. Participants will also be asked to report which type or types of drugs they think they received at each session. Finally, participants will be fully debriefed with regard to the study hypotheses, methods and the types of drugs that they received, and will be given a chance to ask any final questions.

Data Analysis

IAPS: We hypothesize that participants will react less to negative pictures while taking CBD, while reactions to positive and neutral slides will be unchanged. We will conduct a Mixed Linear Model analysis in R using lme4 on each dependent variable (subjective ratings, corrugator and startle responses) using Drug (0, 300, 600 and 900mg) and picture type (positive, neutral, negative) as independent variables, and including random variables for Subject and Drug.

DEIT: We hypothesize that participants will show decreased sensitivity to negative facial expressions (anger, sadness and fear) on CBD, as measured by a greater intensity of expression required to identify negative facial expressions, but unchanged intensity for happy facial expressions. We also hypothesize that CBD will reduce negative psychophysiological responses to negative facial expressions, but not happiness. We will conduct a Mixed Linear Model analysis in R using lme4 on each dependent variable (expression intensity and corrugator responses) using Drug (0, 300, 600 and 900mg) and expression type (happy, angry, fearful, sad) as independent variables, and including random variables for Subject, Drug and Actor.

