3. Tasks: Some of the tasks (emotional pictures, pictures of facial expressions) employ stimuli that are designed to elicit short-term positive and negative emotional reactions. Although the pictures used are designed to elicit emotional reactions, these reactions are typically brief, and similar methods to have previously been used in a wide range of studies without evidence of any long-term adverse reactions. Further, participants are screened for any psychiatric conditions that might make them vulnerable to experiencing adverse reactions to brief alterations in mood. Any participants who are unduly distressed will be counseled by a trained staff member.

Benefits to subjects: There is no direct benefit to the participants, although we hope that the information learned from this study will contribute to our knowledge of factors influencing drug use. Additionally, participating in research may be an educational experience for participants, and we attempt to facilitate this by providing a thorough debriefing including an explanation of study hypotheses and procedures at the conclusion of participation.

Subject time commitment and compensation: The screening portion of the study takes approximately 2 hours. The orientation typically takes approximately 1 hour. The study sessions are estimated to last 5 hrs each, and the debriefing is .5 hours, for a total of 21.5 hours spent in study sessions. Participants are compensated \$35 for each study session, with a bonus of \$110 for completion of all study sessions, giving a total of \$250.

Data and Safety Monitoring: The PI will monitor data collection and safety at weekly staff meetings. During these meetings, the PI will review and respond appropriately to

(1) data collection and storage practices and (2) any adverse or unexpected effects from the study drugs. Both the study physician and PI will monitor the safety of study participants on an ongoing basis. The physician connected with this study will be on call during the experimental sessions and for 24 hours after sessions. Subjects will be given telephone numbers for the study physician and investigators in case they experience unpleasant effects after leaving the laboratory.

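### Adverse effects after participants leave the laboratory are not actively solicited: no procedure listed for later sessions or the debriefing asks about them

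*Combined protocol and SAP*

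**What the plan says.** **How long effects may last.** The Study Session section says: "Some drug effects may persist for up to 12hrs after the end of the study session". The same sentence expects these effects to be mild and not impairing. Under Drug and Doses, plasma levels peak about 1 to 4 hours after an oral dose and "remain elevated up to 12 hr after an acute dose".

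**When observation ends.** "Participants will be administered the drug or placebo at 1:30pm". The Timeline has the last assessment at 5:45pm and departure at 5:50pm. Departure is conditional: participants stay until at least 5:45pm, "or until drug effects decrease sufficiently to permit participants to leave safely (as measured by both subjective report and cardiovascular variables").

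**What covers the time after departure.** Data and Safety Monitoring gives three provisions:
- Telephone contact started by the participant: "Subjects will be given telephone numbers for the study physician and investigators in case they experience unpleasant effects after leaving the laboratory".
- Medical cover: "The physician connected with this study will be on call during the experimental sessions and for 24 hours after sessions".
- A general statement: "Both the study physician and PI will monitor the safety of study participants on an ongoing basis". The PI also reviews adverse or unexpected effects at weekly staff meetings.

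**What later visits collect.** Before the capsule, each session lists a snack, breath and urine screening, a pregnancy test for women, and mood, drug-effect and cardiovascular measures. Obtaining consent adds a verbal check of consent. For the debriefing: "Participants will return to the lab for a final session at which they will complete a final DEQ rating", followed by a guess at the drug types received, an explanation of the study and a chance to ask questions. No question about the interval since the last session appears in any of these lists. No diary, follow-up call or adverse-event form is described.

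**The concern.** The plan recognises a period of possible drug effect that runs well beyond departure, and then relies on the participant to start any report from that period. People are more likely to phone about something severe or frightening than about passing nausea, fatigue or light-headedness, so the milder effects are the ones likely to be missed.

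Two things are at stake. Each participant is due to receive four blinded capsules, and an effect that followed one of them may be unknown to staff when the next is given. Also, any count of events by dose would combine effects seen by staff in the laboratory with effects at home that happened to be reported. The protocol notes that combined CBD/THC products have been studied more for adverse effects than CBD alone, so evenly collected CBD-alone data would be useful here. Weekly review does not fill the gap, because it can act only on events that have reached the team.

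**Working it through.** The plan gives no figure of its own for this point. The check is clock arithmetic on its stated times, followed by a reading of what each later visit lists.

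**Inputs**
- Capsule 1:30pm (Study Session; Timeline).
- Scheduled departure 5:50pm (Timeline).
- Reading A: window ends 12 h after the dose, at 1:30am (Drug and Doses, plasma levels).
- Reading B: window ends 12 h after the session, at about 5:50am (Study Session, drug effects).
- 36 expected completers, three active doses and one placebo each (Subjects; Design).

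**Observed time after the dose**

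1:30pm to 5:50pm = 4 h 20 min = 4.33 h.

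**Share after departure** = (end of window − departure) / (end of window − dose)

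- Reading A: (12 − 4.33) / 12 = 7.67 / 12 = 64%.
- Reading B: 12 / (4.33 + 12) = 12 / 16.33 = 73%.

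**Sensitivity to a later departure.** The plan allows a longer stay. Under Reading B the window moves with departure, so 12 h always remains.

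| Extra stay | Reading A | Reading B |
|---|---|---|
| 0 h | 64% | 73% |
| 1 h | 56% | 69% |
| 2 h | 47% | 65% |
| 4 h | 31% | 59% |

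Under Reading A the share falls below half once departure is later than 7:30pm (1:30pm + 6 h).

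**Position of the peak.** The stated plasma peak of 1 to 4 h ends before 4.33 h, so it lies inside the observed time.

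**Number of post-session periods among completers**
- Active dose: 36 × 3 = 108.
- Placebo: 36 × 1 = 36.
- Total: 144.

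**Which procedure could pick up an event at home**

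| Route | Who starts it | Asks about the interval? |
|---|---|---|
| Telephone numbers | Participant | No |
| On-call physician, 24 h | Participant, in practice | No |
| Weekly PI review | Staff | No; needs an event already reported |
| Pre-capsule measures at next session | Staff | None listed |
| Verbal consent check | Staff | None listed |
| Debriefing | Staff | None listed; participant may raise it |

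No listed route has staff asking about the period after departure.

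**The case against.** The strongest reply is that the period is covered. A physician is on call for 24 hours, longer than either 12-hour window. Participants leave only when effects have decreased on both subjective report and cardiovascular variables. The plasma peak is observed, residual effects are expected to be mild, and most of the listed side effects are attributed to THC, which is not given here. This is a single-dose mechanistic study in screened healthy volunteers with no safety endpoint. The protocol may also simply not write down every question staff ask.

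Much of this stands. A reader might infer that most of the risk period is unmonitored; the documents do not support that. Cover exists, and the 64% and 73% count hours, not risk. What the reply does not supply is any stated step in which someone asks. On-call cover helps those who call. Expected mildness argues against alarm, but mild effects are also the ones least likely to prompt a call. Staff may ask informally, but an unwritten question cannot be relied on to be asked in the same way after every session.

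Other stronger readings also fail:
- **More is missed after higher doses.** Nothing in the documents says duration of effect varies with dose.
- **The questionnaires used in sessions cannot register particular symptoms.** Their items are not reproduced, so this cannot be checked.
- **The gap undermines the statement about less sedation than diazepam.** That statement summarises earlier studies, and this trial has no diazepam arm.
- **A given percentage of events is lost.** The documents give no reporting rate.

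**Conclusion.** The point holds as a gap in solicitation, not as an absence of safety cover. After departure, adverse effects reach the team only if the participant phones or volunteers them later. At the scheduled departure time this applies to 64% of the 12 hours after the dose, or 73% of the time to 12 hours after the session, across 108 active-dose and 36 placebo periods in 36 completers. The placebo periods carry no drug effect but are the comparison for the active ones.

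These figures rest on the 5:50pm departure and shrink with a longer stay. They also rest on reading the visit descriptions as the procedures planned. The separate screening protocol is not available, but it is described as covering screening, so it is not assumed to fill the gap. How many events would be missed cannot be computed. The change is a cheap and worthwhile improvement; the gap does not threaten the study's main aims.

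**What to change.** At the start of sessions 2 to 4, and at the debriefing for session 4, have the research assistant already present ask a brief, neutrally worded question about any unwanted effects since the last session. Use the same wording after every session, so that placebo and active periods are treated alike. Record onset, duration, severity and any action taken. Pass the record to the PI and study physician through the existing monitoring, and tabulate events by dose and by in-laboratory versus after leaving.

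**Cost.** A few minutes at visits already scheduled, with no added visit or staff. More minor events will be recorded, on placebo too. Recall will be imperfect over the interval between sessions, for which the protocol gives two minimums (7 days under Drug and Doses, 5 days under Study Session) that should be reconciled. Naming symptoms could cue expectancy, which the orientation procedure tries to reduce. Asking an open question before any checklist would limit this.

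**Limit.** The question reaches only people who return. Of 50 recruited, 36 are expected to complete, so up to 14 may miss a later visit. Their last post-session period would still depend on their own report unless they attend the debriefing.
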